5.5 Treatment

1. Subjects will be randomized in a 1:1 ratio to receive study drug vs standard plasma
2. Study drug: The investigational product is anti-SARS-CoV-2 convalescent plasma obtained from patients identified as having recovered from COVID-19 with neutralizing antibody titers >1:64.
3. Donors and samples will have been screened for transfusion-transmitted infections (e.g. HIV, HBV, HCV, WNV, HTLV-I/II, *T.cruzi*, ZIKV) both through the use of the uniform donor questionnaire and FDA mandated blood donor screening tests. Plasma will have been collected using apheresis technology and in accordance with standard FDA and blood bank protocols.
4. Active arm will receive 1-2 units of plasma with an anti-SARS-CoV-2 titer of >1:64
5. Control arm will receive 1-2 units of standard plasma.
6. Both active and control drugs will be in standard plasma unit bags, with a study-specific ISBT label.

5.6 Subject Randomization

1. Subjects enrolled in the study will be randomized using an interactive web response system (IWRS) to receive study drug vs placebo at a 1:1 ratio.

6. Rationale for doses

Provisionally going with 1-2 units; ~300-600 mL at neutralization antibody titer >1:64 (*if possible >1:160 this is a moving target as assays develop*)

Standard plasma⁶

For a 70 Kg person plasma volume is estimated at 2800 mL (40 mL/kg x 70 kg) with baseline anti-SARS-CoV-2 titer of 0.

For example, if protective titer was 1:25 and each unit had titer of 1:160, you would need ~500 mL to achieve this $[500/(2800+500)] \times 1:160 = 1:25$

In practical terms this would be 2 units of FFP per patient, would consider 1 unit if the patient is at high risk of circulatory overload.

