PROTOCOL SUMMARY:

Long title: Convalescent Plasma to Limit Coronavirus Associated Complications: A Randomized Open label, Phase 1 Study Comparing the Efficacy and Safety of High-Titer Anti-SARS-CoV-2 plasma vs. placebo in hospitalized patients with interstitial pneumonia due to COVID-19

Short title: CSSC-002

Clinical Phase: 1

IND Sponsor: Johns Hopkins via a national IND

Conducted by: Mayo Clinic in collaboration with Johns Hopkins University, Washington University in St. Louis and other interested parties.

Sample Size: 20

Study Population: Hospitalized COVID-19 patients aged 18 years of age with respiratory symptoms within 3 to 7 days from the beginning of illness.

Study Duration: April 1, 2020 to December 31, 2022

Study Design: This randomized placebo-controlled open label phase 1 trial will assess the efficacy and safety of anti-SARS-CoV-2 convalescent plasma in hospitalized patients with acute respiratory symptoms between 3 and 7 days after the onset of symptoms with or without confirmed interstitial COVID-19 pneumonia by chest CT. A total of 20 eligible subjects will be randomized in a 1:1 ratio to receive either high titer anti-SARS-CoV-2 plasma or control (standard thawed plasma)

The following will be assessed in all subjects:

- Age, sex, comorbidities, date of symptoms, source of infection, type of admission, APACHE score, SOFA score, Clinical status, vital signs including temperature, respiratory rate, oxygen saturation, oxygen requirement, CBC with neutrophil counts, lymphocytes count, CRP, chest x-ray, chest CT, location in hospital,
- Safety and efficacy: Day 0 (baseline), 1, 2, 3, 7, 14, and 28 and once monthly at 2-3 months.
- Serum or plasma antibody titer₁ to SARS-CoV-2: Day 0, 1, 3, 7, 14 (additional days 21 and 28 may be included, as available)

¹ Measured via initial anti-SARS-CoV-2 ELISA and serum neutralizing antibody titer to SARS-CoV-2.

- SARS-CoV-2 PCR from nasopharyngeal swabs: Day 0, 3, 7, 14 and at any time when there is clinical suspicion for COVID-19
- Outcome measures: increased O2 requirement (PaO2/FiO2 ratio or SpO2/Flo2), supplemental oxygen strategy (nasal cannula, , high flow nasal cannula, noninvasive ventilation, intubation and invasive mechanical ventilation, rescue ventilation i.e. neuromuscular blocking agents, prone positioning, corticosteroids, ECMO), vasopressors, renal support, ICU LOS, ICU mortality, Hospital LOS, Hospital mortality, 28 day mortality

Study Agent:

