- Pathogen reduced SARS-CoV-2 convalescent plasma (1-2 units; ~300-600 mL at neutralization antibody titer >1:64 *if possible* >1:160 *this is a moving target as assays develop*)
- Standard plasma²

Primary Efficacy Objective: Reduction in progression of oxygenation and ventilation support

Primary Endpoint: Avoidance of ICU admission.

Secondary endpoints:

1. Cardio-circulatory arrest (at any time)
2. Transfer to ICU
3. Type and duration of respiratory support (and other ICU support)in ICU
4. ICU mortality and LOS
5. Hospital mortality and LOS
6. Ventilator-free days
7. 28 day mortality

Primary Safety Objective: Evaluate the safety of treatment with high-titer anti-SARS-CoV-2 plasma versus control (standard plasma) in hospitalized patients with COVID-19 respiratory symptoms.

Primary Safety Endpoints:

1. Rapid deterioration of respiratory or clinical status on transfusion of SARS-CoV-2 convalescent plasma
2. Cumulative incidence of serious adverse events during the study period: transfusion reaction (fever, rash), transfusion related acute lung injury (TRALI), transfusion associated circulatory overload (TACO), transfusion related infection

² Solvent detergent treated pooled plasma

Secondary Objectives:

1. Compare the anti-SARS-CoV-2 convalescent plasma and control (standard plasma) groups anti-SARS-CoV-2 titers at days 0, 1, 3, 7 and 14 (additional days 21 and 28 may be included, as available).
2. Compare the rates, levels and duration of SARS-CoV-2 RNA in NP swabs using RT-PCR amongst the anti-SARS-CoV-2 convalescent plasma and control (standard plasma) groups at days 0, 3, 7 and 14. Other specimen types may be tested as available (eg., BAL fluid, tracheal secretions, sputum, etc.) or when RT-PCR assays are validated for additional sources (*i.e.*, stool, blood).

Study population:

Inclusion Criteria for Enrollment

1. Patients must be 18 years of age or older
2. Hospitalized with COVID-19 respiratory symptoms and confirmation via COVID-19 SARS-CoV-2 RT-PCR testing. Patient is willing and able to provide written informed consent and comply with all protocol requirements.
3. Patient agrees to storage of specimens for future testing.
4. If female must not be pregnant and/or breastfeeding.

Exclusion Criteria

1. Female subjects with positive pregnancy test, breastfeeding, or planning to become pregnant/breastfeed during the study period
2. Receipt of pooled immunoglobulin in past 30 days

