6.1 Study drug administration

- Drug will be administered after randomization

⁶ Solvent detergent treated pooled plasma

- Infusion rate \leq 500 mL/hour
- Pretreatment to minimize transfusion reactions (e.g. acetaminophen, diphenhydramine) may be given per investigator and clinical care team discretion.
- If an AE develops during infusion, the infusion may be slowed or stopped as per investigator's decision.
 - Most reactions to plasma are relatively minor and the infusion can generally be continued. Infusion site burning and non-allergic systemic effects can generally be managed with slowing of the infusion. Infusion can generally be continued in cases of itching or hives after pausing the transfusion, administering antihistamines, and observing the patient for worsening.
 - Severe allergic reactions such as, bronchospasm and hypotension, and may require discontinuation of the infusion.

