2. Study Plasma Administration: 1-2 units of plasma will be transfused. Time at start and end of infusion will be recorded and Vital signs will be measured immediately prior to infusion, 10-20 minutes after start of infusion, at completion of infusion and 30-60 minutes after the end of the infusion
3. COVID-19 symptom screen (fevers, cough, shortness of breath)
4. Assessment of clinical status (7-point ordinal scale)
5. New medical conditions, concomitant medication, AE evaluation
6. physical examination
7. COVID-19 testing (RT-PCR) from nasopharyngeal, throat and stool (optional) samples
8. Blood typing, CBC, comprehensive metabolic panel, C-reactive protein
9. Serological testing: anti-SARS CoV-2 titers
10. Stored samples for future studies (cytokines, CD4-CD8, HLA-DR)

Day 1-7 (or for duration of hospitalization)

1. Vital signs daily
2. COVID-19 symptom screen (fevers, cough, shortness of breath)
3. Assessment of clinical status (7-point ordinal scale)
4. New medical conditions, AE evaluation
5. physical examination
6. CBC, comprehensive metabolic panel, CRP daily
7. Serological testing: anti-SARS CoV-2 titers
8. Stored samples for future studies

Day 28:

Key issues to consider f/u by phone, alive, at home, in hospital (ICU or not), on supplemental O2 or not, back to work, fully, partially, SNF, nursing home, LTAC0

1. COVID-19 symptom screen (fevers, cough, shortness of breath)
2. Assessment of clinical status (7-point ordinal scale)
3. New medical conditions, AE evaluation

Day 60 and 90:

1. COVID-19 symptom screen (fevers, cough, shortness of breath)
2. Assessment of clinical status (7-point ordinal scale)
3. New medical conditions, AE evaluation

10. Efficacy, virology and PK measures

Clinical Efficacy (ordinal scale)

1. Death/Cardio-circulatory arrest at anytime
2. Transfer to ICU
3. Type and duration of respiratory support (and other ICU support)in ICU
4. ICU mortality and LOS
5. Hospital mortality and LOS
6. Ventilator-free days
7. 28 day mortality

Virologic measures

1. Rates, levels and duration of SARS-CoV-2 RNA in NP swabs by RT-PCR at days 0, 3, 7 and 14. Other specimen types may be tested as available (eg., BAL fluid, tracheal secretions, sputum, etc.) or when RT-PCR assays are validated for additional sources (i.e., stool, blood).

2. Serologic positivity and neutralization antibody titers for anti-SARS-CoV-2 at days 0, 1, 3, 7 and 14 (additional days 21 and 28 may be included, as available).

11. Risks and benefits

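### Matching of plasma volume between arms is not ensured: nothing fixes one or two units before the open-label allocation is known

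*Protocol*

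**What the plan says.** The Protocol Summary describes "This randomized placebo-controlled open label phase 1 trial", with 20 subjects allocated 1:1. Section 6.1 adds: "Drug will be administered after randomization". On Day 0, section 9 lists randomization first and the transfusion second.

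The dosing instructions give the same range to both arms:
- Section 5.5, item 4: "Active arm will receive 1-2 units of plasma with an anti-SARS-CoV-2 titer of >1:64".
- Section 5.5, item 5: "Control arm will receive 1-2 units of standard plasma".
- Section 9, Day 0, item 2: "Study Plasma Administration: 1-2 units of plasma will be transfused".

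The only rule for choosing within that range is in section 6. It starts from an antibody calculation, "For example, if protective titer was 1:25 and each unit had titer of 1:160, you would need ~500 mL to achieve this", and concludes: "In practical terms this would be 2 units of FFP per patient, would consider 1 unit if the patient is at high risk". The risk meant is circulatory overload; high risk is not defined.

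A volume in mL is attached only to the antibody product. The Protocol Summary lists "Pathogen reduced SARS-CoV-2 convalescent plasma (1-2 units; ~300-600 mL", and section 6 gives the same mL beside a neutralizing titer. The control is solvent detergent treated pooled plasma, with no mL in either place. Section 5.5, item 6 says that both products come in standard plasma unit bags.

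TACO is named within the primary safety endpoints (section 8). Section 7.1.1 compares the proportions with an SAE, and with a Grade 3 or higher AE, between arms by Fisher's exact test.

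**The concern.** One unit or two is a twofold choice in the exposure that section 6 itself links to circulatory overload. No step commits the investigator to a number before the arm is known. The protocol's argument for the second unit is to raise the recipient's antibody titer, and that argument has no counterpart for standard plasma. A clinician who is unsure about overload therefore has a reason, found in the protocol, to accept the second unit of convalescent plasma, and no such reason for the control.

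If that happened, the active arm would receive more fluid. An excess of TACO or respiratory deterioration there could then come from volume and not from the convalescent product. Section 12 asks whether the safety of convalescent plasma is higher than, lower than or equal to that of standard plasma, and the comparison could not separate the two causes. With 10 patients per arm, a difference that arises after randomization cannot be reliably adjusted away. If the imbalance ran the other way, it could hide harm.

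**Working it through.** **Inputs from the protocol.** Plasma volume 2800 mL at 70 kg, baseline titer 0, example target 1:25, example product titer 1:160, titer floor 1:64 (sections 5.5 and 6). One to two units are about 300 to 600 mL, so about 300 mL per unit (Protocol Summary and section 6). There are 10 patients per arm.

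**1. The protocol's own figure.** Section 6 uses titer = V/(2800 + V) × T. With V = 500 and T = 160, 500/3300 × 160 = 24.2, against a stated 25. Solved exactly, V = 25 × 2800/(160 − 25) = 519 mL. The stated 500 mL is a fair rounding.

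**2. What a second unit adds in the active arm.**

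| Product titer | 1 unit (300 mL) | 2 units (600 mL) |
|---|---|---|
| 1:160 | 300/3100 × 160 = 15.5 | 600/3400 × 160 = 28.2 |
| 1:64 | 300/3100 × 64 = 6.2 | 600/3400 × 64 = 11.3 |

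The gain is a factor of 1.82 at either titer. At 1:160, one unit misses the example target and two units reach it, so the titer reason is real for convalescent plasma. For the control there is no intended antibody gain.

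**3. What a second unit adds in volume.** One unit is 300/2800 = 10.7% of the assumed plasma volume; two are 600/2800 = 21.4%.

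**4. Possible difference in mean volume.** Let p be the share of an arm given two units, and take 300 mL per unit in both arms. Mean volume is 300 × (1 + p), and the difference is 300 × (p active − p control). The protocol gives no shares; those below are assumptions.

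| Active | Control | Mean mL, active and control | Difference |
|---|---|---|---|
| 90% | 90% | 570 and 570 | 0 |
| 90% | 50% | 570 and 450 | 120 |
| 100% | 50% | 600 and 450 | 150 |
| 100% | 0% | 600 and 300 | 300 |

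**5. Illustration of events.** Suppose TACO risk is r with one unit and 2r with two (assumed). With k of 10 patients given two units, expected events are r × (10 + k). For k = 9 active and k = 5 control:
- r = 1%: 0.19 against 0.15.
- r = 3%: 0.57 against 0.45.
- r = 5%: 0.95 against 0.75.

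Each gap is a fraction of one event. None of these risks is in the document.

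**The case against.** The strongest reply is that the protocol treats the arms alike. The nominal range is identical, section 6's rule is worded per patient, and its only trigger for one unit is a patient characteristic that randomization balances in expectation. Nothing tells clinicians to weigh titer against overload or to give controls less. Section 6 is part of the same protocol, so a range in 5.5 with its criterion in 6 is not a contradiction. This stands: no imbalance is planned, and the rule applied evenly would balance the arms on average. It does not close the gap, because the rule is discretionary, lacks a definition of high risk, and can be applied with the arm known.

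Several stronger readings are tempting and are not supported.
- A reader might infer that volumes are unmatched by design. Items 4 and 5 of section 5.5 give the same range.
- A reader might infer that equal units mean unequal mL, because no control volume is given. The standard unit bags in item 6 point, if anything, toward like units, although they describe the container and not the volume. The missing control mL is a missing detail.
- A reader might infer a biased halting rule, since TACO is a halting event (section 13). An event in either arm triggers the halt; it is not a comparison between arms.
- A reader might infer that Fisher's test compares TACO. It is applied to any SAE and to any Grade 3 or higher AE, and the AE analysis is primarily descriptive.
- A reader might infer bias in the ICU endpoint. A route through fluid overload is plausible, but the document gives nothing from which to size it.

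Finally, section 16 requires doses and treatments to be kept in the medical record, so an imbalance could be seen and listed beside each event. Seeing it would still not remove it.

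**Conclusion.** The point holds as a minor design gap: matching of volume is not ensured. A twofold choice relevant to TACO can be made with the arm known, and the protocol's argument for the larger dose applies to one arm only. The possible mean difference toward the active arm runs from 0 to 300 mL, taking 300 mL per unit in both arms. Where it would fall depends on clinicians' choices, which the document does not give, and it does not show that those choices would differ. The effect on TACO or respiratory deterioration is unknown. The event figures above rest on an assumed share given two units, an assumed one-unit risk, and risk proportional to volume. The protocol's dose arithmetic is not at fault.

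**What to change.** - In section 5.5, items 4 and 5, and in the Day 0 procedures of section 9, apply section 6's rule to both arms: two units, or one if the investigator judges the patient to be at high risk of circulatory overload.
- Have the investigator enter one or two units in the IWRS already named in section 5.6 before the arm is released, and give that number whichever arm is assigned.
- Record the volume infused alongside the start and end times that section 9 already requires.
- As a clarification, state the control volume in mL, matched to the convalescent volume for the same number of units.

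The cost is one IWRS field and a few lines of text. Sample size, titer floor, products and donor pool do not change. The downside is that some control patients may receive a second unit that they would otherwise not have had; the overload exception stays in place for those at high risk.

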6.1 Study drug administration

- Drug will be administered after randomization

⁶ Solvent detergent treated pooled plasma

- Infusion rate \leq 500 mL/hour
- Pretreatment to minimize transfusion reactions (e.g. acetaminophen, diphenhydramine) may be given per investigator and clinical care team discretion.
- If an AE develops during infusion, the infusion may be slowed or stopped as per investigator's decision.
 - Most reactions to plasma are relatively minor and the infusion can generally be continued. Infusion site burning and non-allergic systemic effects can generally be managed with slowing of the infusion. Infusion can generally be continued in cases of itching or hives after pausing the transfusion, administering antihistamines, and observing the patient for worsening.
 - Severe allergic reactions such as, bronchospasm and hypotension, and may require discontinuation of the infusion.

6.2 Concomitant medications will be documented on the CRF

- Prescription medications
- Over the counter medications
- Herbal treatments/nutritional supplements
- Blood products

7. Statistical considerations

7.1 Statistical Analysis

Prepared in conjunction with consulting biostatistician [name], Ph.D. All analyses will be presented by plasma type. Full factorial univariate analyses of variances will be used to determine differences between the groups in the primary outcome variables. Descriptive summaries of continuous and other numeric variables will at least consist of the following summary statistics: median, minimum and maximum values. Categorical variables will be summarized by the frequency and proportion of subjects falling into each category. Unless otherwise indicated, percentages in tables will be column percentages, using the total number of observations in the population ($n=20$), grouped by cohort ($n=10$), as the denominator. Percentages will be rounded to one decimal place, and thus may not always add up to exactly 100%. Clinical laboratory values will be first reported in using International System of Units (SI). Exact confidence intervals for binomial proportions will be derived using the Clopper-Pearson method.

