5.4 Subject Withdrawal

1. Subjects can terminate study participation and/or withdraw consent at any time without prejudice.
2. Randomized subjects who withdraw from the study will not be replaced.
3. The investigator may withdraw subjects if they are lost to follow up, non-compliant with study procedures or if the investigator determines that continued participation in the study would be harmful to the subject or the integrity of the study data
4. Discontinuation of the study: The study sponsor, FDA and IRB all have the right to terminate this study at any time

³ At least 2 assessments of ABO type on file, with one in the 90 days prior to enrollment

⁴ Vital sign testing: Immediately prior to infusion, 10-20 minutes after start of infusion, at completion of infusion and 30-60 minutes after the end of the infusion

⁵ Sites could include nasopharyngeal and throat

⁴The assessments performed on day 28 will be repeated on days 60 and 90.

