7.1.1 Analysis of AE data

Analysis of AE data will primarily be descriptive based on MedDRA coding of events. The proportion of subjects experiencing an SAE and the proportion experiencing a Grade 3 or higher AE will be compared between randomized arms using Fisher's Exact Test.

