7.1.2 Analysis of anti-SARS-CoV-2 titers

Analysis of titers will also primarily be descriptive, comparing the geometric mean titers at days 0, 1, 3, 7 and 14 between the randomized arms.

8. Endpoints

Primary Endpoint: Avoidance of new or ongoing ICU admission.

Secondary endpoints:

1. Cardio-circulatory arrest (at any time)
2. Transfer to ICU
3. Type and duration of respiratory support (and other ICU support) in ICU
4. ICU mortality and LOS
5. Hospital mortality and LOS
6. Ventilator-free days
7. 60 day mortality

Primary Safety Endpoints:

- Rapid deterioration of respiratory or clinical status on transfusion of SARS-CoV-2 convalescent plasma
- Cumulative incidence of serious adverse events during the study period: transfusion reaction (fever, rash), transfusion related acute lung injury (TRALI), transfusion associated circulatory overload (TACO), transfusion related infection

Secondary Endpoints

1. Anti-SARS-CoV-2 titers at days 0, 1, 3, 7 and 14.
2. Rates and duration of SARS-CoV-2 PCR positivity (RT-PCR) at days 0, 3, 7, and 14.

9. Study procedures

Day -1 to 0:

- A. Screening (must be completed before randomization)
- B. Subject informed consent (obtained before performing study related activities)
- C. Baseline Evaluation (at screening) (much of the information will be obtained from the medical record)
 1. Demographics (Age, sex ethnicity, race)
 2. Medical history (timing of exposure to COVID-19 source patient, acute and chronic medical condition, medications, allergies. Any medical condition arising after consent should be recorded as AE)
 3. COVID-19 symptom screen (fevers, cough, shortness of breath), onset of symptoms, source of contagion
 4. Vital signs
 5. COVID-19 testing (RT-PCR) from nasopharyngeal, throat, tracheal aspirate or broncho alveolar lavage and stool (optional) samples
 6. Blood typing, CBC, comprehensive metabolic panel
 7. Serological testing: anti-SARS CoV-2 titers
 8. Stored samples for future studies
 9. Urine or serum pregnancy test for females of childbearing potential. Results from laboratory tests obtained up to 7 days before enrollment may be used for the pregnancy test.
 10. Determination of eligibility as per inclusion/exclusion criteria age, consent, positive for COVID-19, respiratory symptoms, not already an ICU patient,, between day 3 and 7 of first sign of illness (or within 72 hours of admission)

DAY 0:

1. Randomization of eligible subjects

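### ANOVA is prescribed for yes/no primary outcomes with 10 patients per arm; it has no result when there are no events and conflicts with the Fisher test in section 7.1.1

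*Protocol*

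**What the plan says.** Section 7.1 gives one method for the main comparison: "Full factorial univariate analyses of variances will be used to determine differences between the groups in the primary outcome variables". It names no factor other than plasma type. The same paragraph closes by assigning Clopper-Pearson exact intervals to binomial proportions.

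Section 8 defines the outcomes to which that sentence applies:

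- Efficacy: "Primary Endpoint: Avoidance of new or ongoing ICU admission".
- Safety, first item: "Rapid deterioration of respiratory or clinical status on transfusion of SARS-CoV-2 convalescent plasma".
- Safety, second item: "Cumulative incidence of serious adverse events during the study period", followed by a list of transfusion complications.

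Section 7.1.1 says that the proportions of subjects with an SAE, and with an AE of Grade 3 or higher, "will be compared between randomized arms using" Fisher's exact test.

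On size, the Protocol Summary says "A total of 20 eligible subjects will be randomized in a 1:1 ratio", which gives 10 per arm. No significance level, sidedness, power or event rate is stated with it.

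**The concern.** Each of these primary outcomes is recorded per patient as an event that happened or did not. ANOVA is built for a continuous response with roughly normal, equal-variance residuals. With 10 patients per arm and a 0/1 response, an arm with no events has zero variance. If both arms have none, there is nothing to divide by. A factorial model also needs at least two crossed factors, and the design has one.

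Two things are at stake. A rare safety outcome could end the trial with no computable comparison, which is where a safety study most needs a clear statement. And the SAE outcome appears to fall under two tests, one through the general sentence in 7.1 and one through 7.1.1. If they disagree, an analyst could choose between them after seeing the data.

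**Working it through.** **Inputs.** 10 patients per arm (Protocol Summary, section 7.1). One factor with two levels (sections 5.5, 5.6, 7.1). Illustrative event rate of 23%: the ICU admission share printed in Figure 1, a background figure and not a design assumption. Assumed: other event rates as shown, and a two-sided 0.05 level, because the protocol states none. There is no power or sample-size figure in the protocol to reproduce.

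**1. What the ANOVA reduces to.** With one two-level factor it is the pooled two-sample t test on 18 degrees of freedom. For a and b events:

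- Between-arm sum of squares: SSB = 5 × (a/10 − b/10)²
- Within-arm sum of squares: SSW = a(10 − a)/10 + b(10 − b)/10
- F = SSB / (SSW/18), on 1 and 18 df

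**2. No events.** With a = b = 0, SSB = SSW = 0 and F = 0/0. The same happens if all 20 patients have the event. The chance of no event in either arm at a common rate r is (1 − r)²⁰:

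| Rate in both arms | P(no events) |
|---|---|
| 23% | 0.77²⁰ = 0.5% |
| 10% (assumed) | 0.90²⁰ = 12.2% |
| 5% (assumed) | 0.95²⁰ = 35.9% |
| 2% (assumed) | 0.98²⁰ = 66.8% |

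Exact and score methods still give a statement for 0/10 vs 0/10: Fisher p = 1.00; Clopper-Pearson 0 to 30.8% in each arm (upper limit 1 − 0.025^(1/10)); Newcombe interval for the difference −27.8 to +27.8 points.

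**3. ANOVA against Fisher, 0/10 vs 4/10.** SSB = 5 × 0.16 = 0.8; SSW = 4 × 6/10 = 2.4; F = 0.8/(2.4/18) = 6.0; p = 0.025. Fisher: one-tail probability C(10,4)/C(20,4) = 210/4845 = 0.0433, doubled = 0.087.

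**4. All 11 × 11 tables.** At 0.05 the two tests disagree only in these patterns and their mirror images:

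| Events | ANOVA p | Fisher p |
|---|---|---|
| 0 vs 4; 6 vs 10 | 0.025 | 0.087 |
| 1 vs 6; 4 vs 9 | 0.018 | 0.057 |
| 2 vs 7; 3 vs 8 | 0.024 | 0.070 |

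ANOVA is the significant one each time. The chance of landing in such a table is the difference between the two rejection rates: 3.3% − 0.9% = 2.4% at 23% in both arms, 6.9% − 2.1% = 4.8% at 23% vs 10%, and 47.1% − 29.5% = 17.6% at 50% vs 10%.

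**5. Type I error.** By enumeration, ANOVA rejects in 3.3% of trials at a 23% rate in both arms and at most 4.2% (at 50%). Fisher's maximum is 1.3%.

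**The case against.** The strongest defence has three parts. First, a specific subsection normally governs over a general sentence, so 7.1.1 already gives SAE proportions a test that can be computed with no events. Second, near a 23% ICU rate the undefined case is very unlikely for the efficacy endpoint. Third, section 4.1 describes the efficacy aim as preliminary, there is no decision threshold, and the ANOVA does not inflate type I error. All of this stands, and it limits the severity. It does not rescue the sentence: the efficacy endpoint and rapid deterioration on transfusion are left with ANOVA as their only named test, and the reader must guess which rule holds for SAEs.

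Two stronger readings are tempting, and the protocol supports neither.

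*That the trial's confidence intervals will be too narrow.* The protocol never says that intervals come from the ANOVA; for proportions it names Clopper-Pearson. Even an ANOVA interval for the risk difference would not be too narrow in general. Its coverage is 95.8% to 99.9% at equal rates from 5% to 50%. It drops to 77.9% at 5% vs 10%, but that is mostly the no-event table counted as a zero-width interval; without that table it is about 98.5%. At 10% vs 23% it is 90.3%, or about 92.7% without that table, a modest shortfall.

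*That missing patients are silently counted as non-events.* Section 7.1 sets percentages "using the total number of observations in the population ($n=20$), grouped by cohort ($n=10$), as the denominator", and section 5.4 says "Randomized subjects who withdraw from the study will not be replaced". But the first sentence concerns table percentages and allows for exceptions. Nothing in it says how a missing outcome is classified, and that is commonly left to the SAP. Using all randomised patients for ICU and death outcomes would keep the same 10.

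**Conclusion.** The concern holds as a wrong stated method, and it should be fixed. Section 7.1 prescribes for yes/no primary outcomes a model that does not suit them, calls it factorial when there is one factor, and overlaps with a different test in 7.1.1. For ICU avoidance the practical effect is which p-value is reported in borderline tables. For rare safety events it is a sizeable chance of no test at all, 36% at an assumed 5% rate. False positives are not inflated.

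This rests on reading the primary outcome variables as the efficacy and safety endpoints labelled primary in section 8, on counting SAE incidence per patient, and on an assumed two-sided 0.05. If only the efficacy endpoint is meant, the conflict over SAEs disappears. The mismatch between ANOVA and a binary endpoint remains.

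**What to change.** Replace the ANOVA sentence in section 7.1 with text to this effect: *each binary primary endpoint is reported as counts per arm with Clopper-Pearson intervals, the risk difference with a Newcombe 95% interval, and a comparison by Fisher's exact test as in 7.1.1, as preliminary evidence. ANOVA is used for continuous outcomes only.* Drop the words full factorial unless a second factor is named.

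Boschloo's test is an acceptable alternative if it is fixed in advance for all binary primary endpoints and 7.1.1 is aligned with it. It gives p = 0.042 for 0/10 vs 4/10, where Fisher gives 0.087, so the choice cannot be left until the data are seen.

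The cost is one paragraph and no new data or patients. The downside is that Fisher is more conservative than ANOVA. At 50% vs 10%, for example, it rejects in 29.5% of trials against 47.1%.

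### Section 7.1 equates the number of observations with the planned counts of 20 and 10, so visit-level percentages come out too low when results are missing

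*Protocol*

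**What the plan says.** The Protocol Summary plans for 20 patients: "A total of 20 eligible subjects will be randomized in a 1:1 ratio". Section 7.1 then gives a default for tables, "Unless otherwise indicated, percentages in tables will be column percentages", and sets the base of those percentages: "using the total number of observations in the population ($n=20$), grouped by cohort ($n=10$), as the denominator". A separate sentence in the same section adds: "Exact confidence intervals for binomial proportions will be derived using the Clopper-Pearson method". That sentence names neither a denominator nor a confidence level.

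Other sections bear on whether 20 and 10 will be the numbers observed:

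- Section 5.4: "Randomized subjects who withdraw from the study will not be replaced".
- Section 5.6 gives an interactive web response system and a 1:1 ratio, and says nothing further about how the arms are balanced.
- Section 13 (Halting Criteria for the Study) allows enrolment to be stopped for review, so fewer than 20 may be randomised.
- Section 8 makes PCR positivity at days 0, 3, 7 and 14 a secondary endpoint.

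No section gives a different denominator for PCR positivity or for any other visit-level proportion.

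**The concern.** The sentence describes one denominator in two ways, as a count of observations and as the planned sample size. With complete data from 10 patients per arm the two agree. Otherwise they cannot both be followed, and the programmer has to choose. The opening qualifier permits exceptions, but the protocol states none.

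Missing visit results are foreseeable. The Schedule of Events places RT-PCR on days 3, 7 and 14. The section 9 procedures list no RT-PCR under days 1 to 7, have no day 14 entry, and move to telephone follow-up at day 28. Patients who have been discharged, have died or have withdrawn may have no swab.

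At stake is the comparison of virological results between arms. If the printed 10 is used regardless, the percentage positive depends on how many swabs were taken as well as on how many were positive, and arms with different missingness are not compared on the same footing.

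**Working it through.** **Reproducing the plan's figure.** 20 patients at 1:1 gives 20 × 1/2 = 10 per arm. The 20 and 10 in section 7.1 agree with the planned design.

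**Inputs.** Denominator of 10 per arm (section 7.1); Clopper-Pearson limits (section 7.1); 95% confidence (assumed, since the level is not stated). The counts of positive and missing swabs are illustrative, because the protocol gives no missingness rate.

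**Size of the distortion.** With x patients in a category and m results available out of 10,

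x/10 = (x/m) × (m/10).

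Every category is therefore multiplied by the share observed, m/10. With 3 of 10 missing the factor is 0.7, a relative reduction of 30%.

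**Limits.** Lower = Beta quantile(0.025; x, n − x + 1). Upper = Beta quantile(0.975; x + 1, n − x). For x = 0 the lower limit is 0.

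| Positives | Results available | On results available (95% CI) | On fixed 10 (95% CI if the same n is used) |
|---|---|---|---|
| 3 | 7 | 42.9% (9.9 to 81.6) | 30.0% (6.7 to 65.2) |
| 4 | 8 | 50.0% (15.7 to 84.3) | 40.0% (12.2 to 73.8) |
| 4 | 7 | 57.1% (18.4 to 90.1) | 40.0% (12.2 to 73.8) |
| 0 | 7 | 0.0% (0 to 41.0) | 0.0% (0 to 30.8) |

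The point estimate falls by 12.9, 10.0 and 17.1 percentage points in the first three rows. In the last row it does not move, but the upper limit falls from 41.0% to 30.8%.

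**Effect on a comparison.** Suppose one arm has 3 positives among 7 swabbed and the other has 4 among 10. On results available, the percentages are 42.9% and 40.0%. On the fixed 10 they are 30.0% and 40.0%. The order reverses, and the arm with missing swabs now appears to have less PCR positivity.

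**The negative category.** With 3 positive, 4 negative and 3 missing, the fixed denominator gives 30.0% positive and 40.0% negative. Both are scaled by 0.7, and the two sum to 70.0%.

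**Arms that are not 10.** If 12 were randomised to an arm and 6 had an event, the correct figure is 6/12 = 50.0% and the fixed rule gives 6/10 = 60.0%. If enrolment stopped with 8 in an arm and 4 had an event, 4/8 = 50.0% and the fixed rule gives 4/10 = 40.0%. Here patient-level endpoints are affected too.

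**How likely a missing result is.** At an assumed 5%, 10% or 20% missing per patient, independently, the chance of at least one missing among 20 is 1 − 0.95^20 = 64%, 1 − 0.90^20 = 88% or 1 − 0.80^20 = 99%.

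**The case against.** The strongest defence is that the bracketed numbers only illustrate the expected size, that the rule is a default open to exceptions, and that visit-level denominators are usually settled in a statistical analysis plan or table shells, which are not at hand. A sensible analyst would use the observed count, and printed counts would let a reader recompute any percentage. This limits the seriousness of the point but does not remove it: the protocol does state a denominator, and its two descriptions conflict once data are incomplete.

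Several stronger readings are tempting and are not supported:

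- **Missing swabs are counted as negative.** No text says so. Section 7.1 reports the subjects in each category, and a patient without a swab is in neither; the negative percentage falls as well.
- **The arm with more missing data always looks better.** This holds only for an unfavourable category such as PCR-positive. For PCR-negative, that arm looks worse.
- **The exact intervals are misstated.** The Clopper-Pearson sentence names no denominator, so this follows only if the table n is carried over.
- **Withdrawals make 10 wrong everywhere.** For ICU admission, death and SAEs, all patients randomised to the arm is a proper base, so non-replacement alone does no harm. Titers are compared by geometric means (section 7.1.2) and involve no percentage.
- **Unequal arms are likely.** With simple randomisation, an exact 10/10 split has probability C(20,10)/2^20 = 17.6%, and a split of 12/8 or worse 50.3%. The protocol never says that allocation is unrestricted, and details of blocking are commonly kept elsewhere. These figures, and the percentages above 100 that a reader might construct from an arm larger than 10, are not evidence against this plan.

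**Conclusion.** The point holds in a limited form. Section 7.1 ties the percentage denominator to planned counts that need not match the number of observations, and gives no alternative. Applied literally, it understates visit-level categories in proportion to the results missing: by 10 to about 17 percentage points in the illustrations with two or three of ten missing. It can also reverse the apparent ordering of the arms on PCR positivity.

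The size rests on assumed counts and on a literal reading of n=10; the interval figures also assume 95% confidence and that the table n is carried over. Patient-level endpoints are affected only if an arm does not have exactly 10 randomised. No sample-size calculation, hypothesis test or decision rule in the protocol is shown to depend on the sentence. It is a minor reporting correction.

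**What to change.** Amend the denominator sentence in section 7.1:

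- Delete the fixed values of 20 and 10.
- For patient-level endpoints (ICU admission, death, SAE), use the number actually randomised to the arm.
- For visit-level endpoints such as PCR positivity, use the number with a result at that visit, and print that n and the number missing beside the percentage.
- State that the Clopper-Pearson interval uses the same n as the percentage it accompanies.

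The cost is a short text change in one section. It needs no new data, no additional patients and no change to the visit schedule.
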